## Table SCUTS Statistical Comparison of Urge to Smoke VAS Parameters Emax and AUECO-240 Following Controlled Product Use (Outcomes Population)

Programmer note: The table should include all the comparisons of interest listed in Section 8.6.

Product A: < > Product B: < > Product C: < > Product D: < > Product E: < > Test = The first

Test = The first product in the comparison; Reference = The second product in the comparison; n = Number of observations used in analysis The mixed model includes sequence, product, and study period as fixed effects and subject-nested-within-sequence as a random effect. Mixed model with a default (variance component) covariance structure was used. Least-squares means (LS Means) are calculated from the ANOVA.

Source: ADaM.< >

Program: /CAXXXX/sas prg/stsas/tab/programname2022Q1.sas DDMMMYYYY HH:MM

Subscale	Sov	Statistics	a	B	Product -	 م	 ਸ
Satisfaction	Male	n	Х	Х	Х	Х	Х
		n missing	Х	Х	Х	Х	Х
		Mean	X.X	X.X	X.X	X.X	X.X
		SD	X.XX	X.XX	X.XX	X.XX	X.XX
		CV (%)	XX.X	XX.X	XX.X	XX.X	XX.X
		SEM	X.XX	X.XX	X.XX	X.XX	X.XX
		Minimum	XX	XX	XX	XX	XX
		Q1	X.X	X.X	X.X	X.X	X.X
		Median	X.X	X.X	X.X	X.X	X.X
		Q3	X.X	X.X	X.X	X.X	X.X
		Maximum	XX	XX	XX	XX	XX
		95% CI	х.х-х.х	X.X-X.X	х.х-х.х	х.х-х.х	х.х-х.х

Table PESS Summary of PES Factor Scores Following Controlled Product Use by Sex and Product (Outcomes Population)

<Similar to above for all subscales and Sex = Female and Overall>

Programmer note: The table should include all the Subscales listed in Section 9.2.

Product A: < > Product B: < > Product C: < > Product D: < > Product E: < >

Source: ADaM.< > Program: /CAXXXX/sas\_prg/stsas/tab/programname2022Q1.sas DDMMMYYYY HH:MM

				Product -		
Sex	Statistics	A	В	С	D	E
Male	n	X	х	Х	х	Х
	n missing	Х	Х	Х	Х	Х
	Mean	X.X	X.X	X.X	X.X	X.X
	SD	X.XX	X.XX	X.XX	X.XX	X.XX
	CV (%)	XX.X	XX.X	XX.X	XX.X	XX.X
	SEM	X.XX	X.XX	X.XX	X.XX	X.XX
	Minimum	XX	XX	XX	XX	XX
	Q1	X.X	X.X	X.X	X.X	X.X
	Median	X.X	X.X	X.X	X.X	X.X
	Q3	X.X	X.X	X.X	X.X	X.X
	Maximum	XX	XX	XX	XX	XX
	95% CI	х.х-х.х	х.х-х.х	х.х-х.х	X.X-X.X	х.х-х.х

Table ITUS Summary of Intent to Use VAS Raw Scores Following Controlled Product Use by Sex and Product (Outcomes Population)

<Similar to above for Sex = Female and Overall>

Programmer note: Table 14.2.3.3.2 will resemble the shell above with bipolar scores.

Product A: < > Product B: < > Product C: < > Product D: < > Product E: < >

Source: ADaM.< > Program: /CAXXXX/sas\_prg/stsas/tab/programname2022Q1.sas DDMMMYYYY HH:MM

				Product -		
Bipolar Score		A	В	С	D	E
Category	Sex	(N = X)	(N = X)	(N = X)	(N = X)	(N = X)
-50 to <0	Male	X (XX%)	X ( XX%)	X ( XX%)	X (XX%)	X (XX%)
	Female	X ( XX%)	X ( XX%)	X ( XX%)	X ( XX%)	X ( XX%)
	Overall	X ( XX%)	X ( XX%)	X ( XX%)	X ( XX%)	X ( XX%)
0	Male	X ( XX%)	X ( XX%)	X ( XX%)	X ( XX%)	X ( XX%)
	Female	X ( XX%)	X (XX%)	X (XX%)	X ( XX%)	X ( XX%)
	Overall	X ( XX%)	X ( XX%)	X ( XX%)	X ( XX%)	X ( XX%)
>0 to 50	Male	X ( XX%)	X ( XX%)	X ( XX%)	X ( XX%)	X (XX%)
	Female	X ( XX%)	X (XX%)	X ( XX%)	X ( XX%)	X ( XX%)
	Overall	X (XX%)	X (XX%)	X (XX%)	X (XX%)	X (XX%)

Table ITUF Frequency of Intent to Use VAS Bipolar Scores in Each Category Following Controlled Product Use by Sex and Product (Outcomes Population)

Product A: < > Product B: < > Product C: < > Product D: < > Product E: < >

Source: ADaM.< >

Program: /CAXXXX/sas\_prg/stsas/tab/programname2022Q1.sas DDMMMYYYY HH:MM

		-			Product		
Parameter (units)	Sex	Statistics	A	В	С	D	E
Total Puff Number	Male	n	X	X	х	X	х
		n missing	Х	Х	Х	Х	Х
		Mean	X.X	X.X	X.X	X.X	X.X
		SD	X.XX	X.XX	X.XX	X.XX	X.XX
		CV (%)	XX.X	XX.X	XX.X	XX.X	XX.X
		SEM	X.XX	X.XX	X.XX	X.XX	X.XX
		Minimum	XX	XX	XX	XX	XX
		Q1	X.X	X.X	X.X	X.X	X.X
		Median	X.X	X.X	X.X	X.X	X.X
		Q3	X.X	X.X	X.X	X.X	X.X
		Maximum	XX	XX	XX	XX	XX
		95% CI	X.X-X.X	х.х-х.х	X.X-X.X	Х.Х-Х.Х	Х.Х-Х.Х

Table PUFS Summary of Per-Product Puff Topography Parameters by Sex and Product (Outcomes Population)

<Similar to above for all Parameters and Sex = Female and Overall>

Programmer note: The table should include all the per-product parameters listed in Section 10.

Product A: < >

Product B: < >

Product C: < > Product D: < >

Product E: < >

Source: ADaM.< >

Program: /CAXXXX/sas prg/stsas/tab/programname2022Q1.sas DDMMMYYYY HH:MM

Table SPUFS Statistical Summary of Per-Product Puff Topography Parameters Following Ad Libitum Product Use (Outcomes Population)

Product	Parameter (Units)	n	LS Mean	95% Confidence Interval
A	Total Puff Number	X		 XX.XX - XXX.XX
	Total Puff Duration (s)	Х	X.XXX	XX.XX - XXX.XX
	Average Puff Duration (s)	Х	X.XXX	XX.XX - XXX.XX
	Total Puff Volume (mL)	Х	X.XXX	XX.XX - XXX.XX
	Average Puff Volume (mL)	Х	X.XXX	XX.XX - XXX.XX
	Average Peak Flow Rate (mL/s)	Х	X.XXX	XX.XX - XXX.XX
	Average Flow Rate (mL/s)	Х	X.XXX	XX.XX - XXX.XX
	Total Inter-puff Interval (s)	Х	X.XXX	XX.XX - XXX.XX
	Average Inter-puff Interval (s)	Х	X.XXX	XX.XX - XXX.XX

<Similar to above for Products>

Product A: < >

Product B: < >

Product C: < >

Product D: < >

Product E: < >

n = Number of observations used in analysis

The mixed model includes sequence, product, and study period as fixed effects and subject-nested-within-sequence as a random effect. Mixed model with a default (variance component) covariance structure was used. Least-squares means (LS Means) are calculated from the ANOVA.

Source: ADaM.< > Program: /CAXXXXX/sas prg/stsas/tab/programname2022Q1.sas DDMMMYYYY HH:MM

Table SCUFS	Statistical	Comparison of	Urge t	o Smoke	VAS 1	Parameters	Emax	and AUECO-240	Following	Controlle	ed Proc	duct U	se
				(Out	come	s Populatic	n)						
			-		- LS I	Mean		LS Mean Diffe	erence				
						-					-		-

		Шĸ	5 Picari	Do ricuit Diriciciice		
Comparison	Parameter (Units)	Test (n)	Reference (n)	(Test - Reference)	95% Confidence Interval	p-value
Product A vs Product E	Total Puff Number	X.XX (X)	X.XX (X)	X.XXX	XX.XX - XXX.XX	x.xxxx
	Total Puff Duration (s)	X.XX (X)	X.XX (X)	X.XXX	XX.XX - XXX.XX	X.XXXX
	Average Puff Duration (s)	X.XX (X)	X.XX (X)	X.XXX	XX.XX - XXX.XX	X.XXXX
	Total Puff Volume (mL)	X.XX (X)	X.XX (X)	X.XXX	XX.XX - XXX.XX	X.XXXX
	Average Puff Volume (mL)	X.XX (X)	X.XX (X)	X.XXX	XX.XX - XXX.XX	X.XXXX
	Average Peak Flow Rate (mL/s)	X.XX (X)	X.XX (X)	X.XXX	XX.XX - XXX.XX	X.XXXX
	Average Flow Rate (mL/s)	X.XX (X)	X.XX (X)	X.XXX	XX.XX - XXX.XX	X.XXXX
	Total Inter-puff Interval (s)	X.XX (X)	X.XX (X)	X.XXX	XX.XX - XXX.XX	X.XXXX
	Average Inter-puff Interval (s)	X.XX (X)	X.XX (X)	X.XXX	XX.XX - XXX.XX	X.XXXX

Programmer note: The table should include all the comparisons of interest listed in Section 8.6.

Product A: < >

Product B: < > Product C: < >

Product D: < >

Product E: < >

Test = The first product in the comparison; Reference = The second product in the comparison; n = Number of observations used in analysis The mixed model includes sequence, product, and study period as fixed effects and subject-nested-within-sequence as a random effect. Mixed model with a default (variance component) covariance structure was used. Least-squares means (LS Means) are calculated from the ANOVA.

Source: ADaM.< >

Program: /CAXXXXX/sas prg/stsas/tab/programname2022Q1.sas DDMMMYYYY HH:MM

#### ----- Product -----С Sex Statistics Α В D \_\_\_\_ \_\_\_ Х Х Х Х Male n Х n missing Х Х Х X.X Mean X.X X.X X.X SD X.XX X.XX X.XX X.XX CV (%) XX.X XX.X XX.X XX.X SEM X.XX X.XX X.XX X.XX Minimum XX XX XX XX 01 X.X X.X X.X X.X Median X.X X.X X.X X.X Q3 X.X X.X X.X X.X Maximum XX XX XX XX 95% CI X.X-X.X X.X-X.X X.X-X.X X.X-X.X

Table PUBS Summary of Total Number of HTP/HHP Sticks Used During the Ad Libitum Product Use by Sex and Product (Outcomes Population)

<Similar to above for Sex = Female and Overall>

Product A: < >
Product B: < >
Product C: < >
Product D: < >
HTP = Heated tobacco product; HHP = Heated herbal product

Source: ADaM.< >

Program: /CAXXXXX/sas prg/stsas/tab/programname2022Q1.sas DDMMMYYYY HH:MM

Table SPUBS Summary of Total Number of OBCCs on Days -1 through 5 During the Ad Libitum Product Use by Sex and Study Period (Outcomes Population)

			-				
Sex	Statistics	Check-in	1	2	3	4	Overall
Male	n	х	Х	X	X	X	х
	n missing	Х	Х	Х	Х	Х	Х
	Mean	X.X	X.X	X.X	X.X	X.X	X.X
	SD	X.XX	X.XX	X.XX	X.XX	X.XX	X.XX
	CV (응)	XX.X	XX.X	XX.X	XX.X	XX.X	XX.X
	SEM	X.XX	X.XX	X.XX	X.XX	X.XX	X.XX
	Minimum	XX	XX	XX	XX	XX	XX
	Q1	X.X	X.X	X.X	X.X	X.X	X.X
	Median	X.X	X.X	X.X	X.X	X.X	X.X
	Q3	X.X	X.X	X.X	X.X	X.X	X.X
	Maximum	XX	XX	XX	XX	XX	XX
	95% CI	X.X-X.X	X.X-X.X	X.X-X.X	X.X-X.X	X.X-X.X	X.X-X.X

<Similar to above for Sex = Female and Overall>

OBCC = Subject's Own Brand Combustible cigarette

Source: ADaM.< > Program: /CAXXXXX/sas prg/stsas/tab/programname2022Q1.sas DDMMMYYYY HH:MM

				Product	;	
Sex	Statistics	A	В	С	D	E
Male	n	X	X	х	X	X
	n missing	Х	Х	Х	Х	Х
	Mean	X.X	X.X	X.X	X.X	X.X
	SD	X.XX	X.XX	X.XX	X.XX	X.XX
	CV (%)	XX.X	XX.X	XX.X	XX.X	XX.X
	SEM	X.XX	X.XX	X.XX	X.XX	X.XX
	Minimum	XX	XX	XX	XX	XX
	Q1	X.X	X.X	X.X	X.X	X.X
	Median	X.X	X.X	X.X	X.X	X.X
	Q3	X.X	X.X	X.X	X.X	X.X
	Maximum	XX	XX	XX	XX	XX
	95% CI	X.X-X.X	Х.Х-Х.Х	X.X-X.X	X.X-X.X	X.X-X.X

Table SCPUB Summary of Total Number of Puffs During the Controlled Product Use by Sex and Product (Outcomes Population)

<Similar to above for Sex = Female and Overall>

Product A: < > Product B: < > Product C: < > Product D: < > Product E: < >

Source: ADaM.< > Program: /CAXXXX/sas\_prg/stsas/tab/programname2022Q1.sas DDMMMYYYY HH:MM

#### Table CAES Product Use-Emergent Adverse Event Frequency by Product -Number of Subjects Reporting the Event (% of Subjects Who Received Study Product) (Safety Population)

Adverse Event	Product Trial* (N = X)	A (N = X)	B (N = X)	C (N = X)	D (N = X)	(N = X)	Overall# (N = X)	
Number of Subjects With PUEAEs Number of Subjects Without PUEAEs	X ( X%) XX ( XX%)	X ( XX%) XX ( XX%)	X ( XX%) XX ( XX%)	X ( XX%) XX ( XX%)	X ( XX%) XX ( XX%)	X ( XX XX ( XX	5) X (XX%) 5) X (XX%)	
Eye disorders Vision blurred	X ( X%) X ( X%) X ( X%)	X ( X%) X ( X%)	X ( X%) X ( X%)	X ( X%) X ( X%)	X ( X%) X ( X%)	X ( X9 X ( X9 X ( X9	5) X (XX%) 5) X (XX%)	
Dyspepsia Nausea	X ( X%) X ( X%) X ( X%)	X ( X8) X ( X8) X ( X8)	X ( X3 X ( X3 X ( X3	5) X (XX8) 5) X (XX8) 5) X (XX8)				
Musculoskeletal and connective tissue disorders Back pain	X ( X%) X ( X%)	X ( X% X ( X%	5) X ( XX%) 5) X ( XX%)					
Muscle cramps Musculoskeletal pain	X ( X%) X ( X%) X ( X%)	X ( X%) X ( X%) V ( X%)	X (X X (X V (X	5) X (XX%) 5) X (XX%)				
Headache	X ( X%)	X ( X	$\begin{array}{c} x \\ x $					

Product A: < >

Product B: < >

Product C: < >

Product D: < >

Product E: < >

Although a subject may have had 2 or more adverse events, the subject is counted only once within a category. The same subject may appear in different categories.

Adverse events are classified according to MedDRA Version 26.1.

\*Only includes subjects that enrolled in the Product Trial period and dropped prior to randomisation.

#Subjects who only participated in the Product Trial period are not included in the Overall summary.

PUEAEs = Product use-emergent adverse event

Source: ADaM.< >

Program: /CAXXXX/sas prg/stsas/tab/programname2022Q1.sas DDMMMYYYY HH:MM

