6.4.5.2 Reporting

All AEs occurring during this clinical trial after the subject has received the first study product (i.e., at the Product Trial) must be recorded on the CRF, including the date and time of onset, action taken, outcome (resolved, improved, unchanged, worse, fatal, or unknown/lost to follow-up), duration, relationship to product administration, and severity for each event. AEs will be listed.

Events captured between Screening and the first study product use will be documented as baseline signs and symptoms.

The Investigator will review each event and assess its relationship to product administration as unrelated, unlikely, possibly, probably, or likely.

In addition, each sign or symptom reported will be graded on a 3-point severity scale using mild, moderate, or severe.

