#### Visit 2 (In-clinic period, Day -1 to Day 5)

At Visit 2, subjects who successfully complete the screening procedures and meet all the inclusion criteria and none of the exclusion criteria will be eligible to check in to the clinical research unit (CRU) on Day -1 and will remain at the clinic until Day 5 for daily study

product use, PK sampling, subjective questionnaire assessments, puff topography (as applicable), and safety assessments.

On Day -1, following eligibility confirmation, subjects will undertake a familiarisation session of the study products and questionnaires. The clinical team will explain how the HTPs and HHPs will be used. Subjects will have the opportunity to see the products/devices and packaging and will participate in a Product Trial where they will take 5 puffs on a single one HTP stick (flavour chosen by subject) and 5 puffs on a single HHP stick (flavour chosen by subject). All products/devices used in the trial session will not be used in the clinical study but will be retained as demonstration samples for accountability purposes. An explanation of how the questionnaires will be administered to the subjects will be given. After the familiarisation session and completion of check-in procedures, subjects will be allowed to smoke their own cigarettes *ad libitum* but will abstain from use of any tobacco- or nicotine-containing products for at least 12 hours prior to the start of the morning controlled product use session on Day 1.

In the morning of Days 1 through 5, after pre-use assessments and confirmation of eligibility, subjects will use their randomly-assigned study product under controlled conditions by completely using a single unit (one stick, approximately 10 puffs) of the assigned study product, with puffs taken at 30-second intervals and of 3-second duration. PK samples will be collected within 5 minutes pre-study product use (timepoint '0') and at 2, 4, 6, 8, 10, 15, 30, 45, 60, 120, and 240 minutes following the start of study product use. Questionnaires will be administered to the subject at defined intervals throughout the day. Safety will be monitored throughout the day.

On Days 1 through 5, following the 4-hour PK blood collection, subjects will start a 4-hour *ad libitum* product use session (no limits on cigarette, HTP or HHP consumption) with the same study product used during the morning controlled use session.

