## **12. SAFETY**

All relevant case report form (CRF) and clinical laboratory data will be listed by subject and chronologically by assessment time point. This will include rechecks, unscheduled, and early termination assessments.

Applicable continuous variables will be summarised using n, mean, SD, minimum, median, and maximum.

The level of precision will be presented as follows: minimum/maximum in the same precision as in the database, mean/median in one more precision level than minimum/maximum, SD in one more precision level than mean/median, and n will be presented as an integer. Percentages will be presented as an integer.

Where individual data points are missing because of dropouts or other reasons, the data will be summarised based on reduced denominators.

Baseline will be the result closest and prior to the first product use on Day 1 unless otherwise stated. Summaries for post-baseline time points will not include rechecks, unscheduled, or early termination measurements.

Tables summarising safety data by assessment time point will only include summaries for baseline and post-baseline time points.

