# 12.5 Adverse Events

All AEs occurring during this clinical trial will be coded using the Medical Dictionary for Regulatory Activities (MedDRA®), Version 26.1.

All AEs captured in the database will be listed in a by-subject data listing including verbatim term, coded term, product, onset date/time, resolution date/time, frequency, severity, relationship to study product, and action; however, only product use-emergent AEs (PUEAEs) will be summarised.

PUEAE is defined as an AE that is starting or worsening at the time of or after the first study product use. Each PUEAE will be attributed to a product based on the onset date and time of

the AE compared to that of the respective product administration date and time. An AE that occurs between products will be considered product use-emergent to the last product administered prior to onset of the AE. AEs occurring prior to the first product use episode on Day 1 but after the product trial has started on Day -1 will be attributed to the product trial.

If the onset time of an AE is missing and the onset date is the same as a product use date, then the AE will be considered product use-emergent in the prior and current product. If the onset time of an AE is missing and the onset date does not fall on a product use date, then the AE will be considered product use-emergent for the last product administered. If the onset date of an AE is missing, then the AE will be considered product use-emergent and attributed to each product on the study, unless the onset date is known to have occurred within or between specific product use periods.

PUEAEs will be tabulated by System Organ Class (SOC) and Preferred Term. Summary tables will include the number of subjects reporting the PUEAE and as a percent of the number of subjects that used study product by product and overall. The number of PUEAEs will be tabulated in a similar manner. A table, which summarises the number of PUEAEs by Preferred Term, severity, and relationship to study product, will also be included.

Serious adverse events (SAEs), if present, will also be listed. Applicable narratives will be included in the CSR.

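### The adverse event shells restrict the Product Trial column to pre-randomisation dropouts, so a randomised subject's trial-period event, which SAP 12.5 assigns to the trial, has no by-product place

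*SAP*

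**What the plan says.** **Attribution.** SAP 12.5 covers events before first product use on Day 1 "but after the product trial has started on Day -1 will be attributed to the product trial". It makes no distinction between subjects who go on to be randomised and those who do not.

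**Emergence.** The same section states: "PUEAE is defined as an AE that is starting or worsening at the time of or after the first study product use". Protocol 6.4.5.2 places that starting point on Day -1, since it requires that events "after the subject has received the first study product (i.e., at the Product Trial) must be recorded on the CRF".

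**Exposure.** Under SAP 3 (Visit 2), subjects "will participate in a Product Trial where they will take 5 puffs on a single one HTP stick", and they take five more puffs on an HHP stick.

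**Tabulation.** SAP 12.5 calls for the number of subjects reporting each PUEAE, also expressed "as a percent of the number of subjects that used study product by product and overall".

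**Shells.** Tables CAES, CAEE and CAESR in SAP 15.2 each have a Product Trial column or row marked with an asterisk, which the footnote explains as "Only includes subjects that enrolled in the Product Trial period and dropped prior to randomisation". The footnote to Overall reads "Subjects who only participated in the Product Trial period are not included in the Overall summary".

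**The concern.** The text and the shells give different rules for the same column. A programmer who follows 12.5 puts a randomised subject's Day -1 event under Product Trial. One who follows the shell leaves it out.

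Tolerability and safety of each product is a secondary objective, and the trial is each subject's first use of the heated products in the study. If the shells are followed, the column meant for events after that use is closed to nearly everyone who had it. With no pre-randomisation dropouts the column would be empty, however many events occurred.

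**Working it through.** No figure in the plan needs reproducing. The check sets the rules side by side and then tallies.

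**Step 1: is a trial-period event a PUEAE?** Yes. SAP 12.5 counts from first study product use, and protocol 6.4.5.2 identifies the trial as the first study product. The shells agree, since they put a Product Trial column in tables of product use-emergent events.

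**Step 2: where does each event go?** Take an event that starts after the trial begins on Day -1 and before first use on Day 1.

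| Subject | SAP 12.5 assigns to | Product Trial column (asterisk footnote) | A to E | Overall |
|---|---|---|---|---|
| Dropped before randomisation | Product Trial | Shown | No | Excluded by footnote |
| Randomised | Product Trial | Barred | No, onset precedes Day 1 use | Not stated |

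The second row is the conflict: no by-product column or row can hold the event. The documents place randomisation on Day -1 (protocol 4.5, SAP 5) and also on Day 1 (protocol Table 1, note h). The result is the same either way.

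**Step 3: who is barred?** SAP 5 plans 5 sequences × 5 subjects = 25 randomised subjects, and all 25 are barred. Let d be the number who drop after the trial and before randomisation. The documents give no value, so d = 0, 1 and 2 are assumed. If everyone takes the trial puffs and no one is replaced:

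- N in CAES under the footnote = d: 0, 1, 2.
- All trial users = 25 + d: 25, 26, 27.

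CAES is the only one of the three AE shells that prints an N.

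**Step 4: do the columns and Overall tie in CAEE?** Consider events attributed to a single product. Let S be the sum of events under A to E, k the trial-period PUEAEs of randomised subjects, and t those of trial-only subjects.

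- Present shells: Product Trial = t and A to E = S. If Overall counts the k events, Overall − S = k, with no column to explain the difference. If it does not, the k events are in no column of CAEE at all.
- Column widened, Overall defined as S + k: Product Trial + A to E = (k + t) + S. Subtracting Overall leaves t, so widening the column alone still leaves a mismatch unless t is reported.

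No AE rate is given, so neither k nor t can be estimated.

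**The case against.** The strongest reply is SAP 15, which says the shells show general layout, may change and may not reflect every aspect of the study. The asterisk footnote also stands under the disposition, demographic and smoking-history shells. It fits there: each subject belongs to one column, and SAP 12.4 summarises trial-only subjects separately. Carry-over from those shells is a plausible explanation, and the body text already has a workable rule. This lowers the weight of the point. It does not remove the conflict, because SAP 15 permits a correction without making one, and the restriction is explicit in all three AE shells.

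A second reply is that nothing is hidden. The footnote is printed under each table, Table SDS shows trial use by subject, the AE listing gives onset and time from last product use, and serious events have their own table. That stands, and it limits the risk of misreading. A listing is still not the by-product tabulation that 12.5 calls for.

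A reader might infer more than the documents support:

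- **That 12.5 fixes the trial denominator.** It bases percentages on users of study product by product. SAP 7 and 12.1 name the products as A to E, and no Product Trial denominator is spelled out. All trial users is the sensible choice, but not a stated rule.
- **That Overall certainly contains these events.** The footnote removes trial-only subjects and is silent on randomised subjects' trial-period events.
- **That the device malfunction table has the same conflict.** It carries the same footnote, but the attribution rule in 12.5 covers AEs only and SAP 12.12 has no trial rule for the footnote to contradict.

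**Conclusion.** The conflict is real and minor. As written, SAP 12.5 and the asterisk footnote in CAES, CAEE and CAESR cannot both be followed for a randomised subject with a trial-period PUEAE.

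Its size is structural: 25 of 25 planned randomised subjects are barred from the column or row. The N of 25 + d for trial users assumes that everyone used a trial product and that there were no replacements. SAP 3 says subjects will not be forced to use products, so the actual number of users should be counted.

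It would be wrong to conclude that the events are lost or that the product comparison is distorted. The by-subject listing keeps them, and counts under A to E do not change. The trial column also pools one HTP and one HHP stick, so it could not attribute an event to A, B, C or D in any case.

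**What to change.** 1. In Tables 14.3.1.1 to 14.3.1.3, replace the asterisk footnote so that the Product Trial column or row includes all subjects who used a trial product on Day -1. Use that number as N in 14.3.1.1.
2. Reword the Overall footnote in the same tables to say that Overall includes randomised subjects' trial-period PUEAEs and excludes those of trial-only subjects.
3. Report the trial-only subjects' events separately, for example as a count in a footnote, so that the columns and Overall tie.

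Leave the footnote as it is in the disposition, demographic and smoking-history shells. Narrowing 12.5 to match the present footnote would also remove the contradiction, but it would leave randomised subjects' trial events without a by-product place.

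The cost is two footnotes in three shells, one N in one shell and one extra count. No new data are needed: the planned listings already give trial use times (Appendix 16.2.5.2) and AE onset times (Appendix 16.2.7.1) by subject.
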